9.1.3 Per-Protocol set

The per-protocol set (PPS) consists of all patients in the study, who received the study implant according to the study protocol, completed the study (Visit 1 to Visit 7) and the measurements of the primary variable is available. Patients with major protocol deviations (e.g. deviations from inclusion/exclusion criteria) will be excluded from this population. The primary and secondary analyses will be performed with the PPS as supportive analysis.

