6.1 Visit Windows

Patients need to be seen within the visit windows as stated in Table 3.

Table 3: Visit Days and Windows

Visit#	Visit Name	Visit Day and Window	
Visit 1	Screening	Up to 2 months before implant placement	
Visit 2	Implant Placement (Baseline)	Day 0	
Visit 3	Suture Removal	7 to 14 days after implant placement	
Visit 4	Provisional Crown 6 weeks ± 2 weeks after implant pla		
Visit 5	sit 5 Final Crown 4 months ± 1 month after implan		
Visit 6	6-month Follow-Up	6 months ± 1 month after implant placement	
Visit 7	12-month Follow-Up (Primary Endpoint)	1) 12 months ± 1 month after implant placement	

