8.5 Pregnancy

If a female patient becomes pregnant during the course of the study, the study visits should be completed as scheduled. Any study assessments that could potentially interfere with the pregnancy should be avoided until after the pregnancy (e.g., radiographs, etc.). The pregnancy should be recorded as an AE, whereas the start of pregnancy will be recorded as the start date of the AE and the date of child birth will be recorded as the end date. Furthermore, the outcome of the pregnancy should be documented.

9 Statistical Considerations

A qualified statistician will perform all statistical analyses.

Since the purpose of this study is descriptive, there are no formal sample size calculations based on comparative hypothesis testing. Statistical analyses will be descriptive (e.g., reporting means, standard deviations, medians, minima, and maxima for continuous variables and patient counts, frequencies and percentages for categorical variables).

The primary analysis will be conducted after all patients completed the 12-month Follow-Up Visit. Baseline is implant placement.

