9.1.2 Full analysis set

The full analysis set (FAS) consists of all patients in the study, who received the study implant and from whom at least one follow-up measurement after baseline is available. This analysis will include patients regardless of any protocol deviations and/or premature termination. The primary analysis will be performed by the intent-to-treat principle with the FAS.

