11.3.5 Early Withdrawal

Any patient may withdraw from the study any time without prejudice and will be offered an alternative treatment related to their dental condition. Patients will be advised of the need for the prescribed follow-up visits for their ongoing care and well-being.

The Investigator may withdraw any patient from the study in the case of:

- Non-compliance with the protocol
- Failure to attend the follow-up visits
- SAE or AE, which in the opinion of the Investigator prevents the patient's further participation in the study.

The Investigator must withdraw any patient from the study in the case of:

Implant loss

The patient withdrawal will be documented on a Study Termination eCRF page and must include the reason for the patient withdrawal. Withdrawn patients will not be replaced and cannot be re-enrolled.

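### The per-protocol set requires completion of Visits 1 to 7, but implant loss forces withdrawal, so losses withdrawn before Visit 7 are dropped and supportive survival and success are biased upward

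*Combined protocol and SAP*

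**What the plan says.** Section 9.1.3 (Per-Protocol set) requires that the implant was placed according to the protocol and that the patient "completed the study (Visit 1 to Visit 7) and the measurements of the primary variable is available". It also excludes major protocol deviations. On the use of the set it says: "The primary and secondary analyses will be performed with the PPS as supportive analysis".

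Section 11.3.5 (Early Withdrawal) says "The Investigator must withdraw any patient from the study in the case of" implant loss, the only mandatory reason listed there. Withdrawn patients are neither replaced nor re-enrolled. On documentation: "The patient withdrawal will be documented on a Study Termination eCRF page and must include the reason for the patient withdrawal".

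Section 7.14 defines a failed implant as one that was removed or is irreparably fractured. Section 7.13 classes every failed implant as not successful.

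Section 9.1.2 assigns the primary analysis to the FAS, and says of it: "This analysis will include patients regardless of any protocol deviations and/or premature termination".

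Table 3 in section 6.1 places Visit 6 at "6 months ± 1 month after implant placement" and Visit 7 at "12 months ± 1 month after implant placement", with no visit between them.

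**The concern.** A per-protocol set normally leaves out patients whose treatment or conduct departed from the protocol. Here the patient may have been treated exactly as planned, the investigator withdrew the patient because the protocol demands it, and the 12-month outcome is already known to be failure. The patient is excluded all the same, and the reason is the primary event itself.

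The analysis meant to support the survival result therefore omits some of the failures it should count. The same patients are non-successes, so the supportive implant success percentage is affected too. For these losses the error runs in one direction only. In a descriptive study the reported percentages are the result, and a reader who sees a PPS survival of 100% could take it as confirming the FAS figure when the set's definition has produced it.

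**Working it through.** **Plan's own figure.** There is none to reproduce. Section 9 states: "Since the purpose of this study is descriptive, there are no formal sample size calculations based on comparative hypothesis testing". No expected loss rate is given.

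**Which failures are dropped**

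| Failure | Withdrawal under 11.3.5 | Visit 7 completed | In PPS as written |
|---|---|---|---|
| Loss leading to withdrawal before Visit 7 | Mandatory | No | No |
| Failure first found at an attended Visit 7 | Too late to prevent Visit 7 | Yes | Possibly |
| Irreparable fracture, implant not removed | Unclear, because implant loss is not defined | Possible | Possibly |

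Only the first row is at issue.

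**Inputs**
- N = 40 implants, the minimum enrolment in section 3.5, with one assessed implant per patient (section 3.3).
- k = losses withdrawn before Visit 7 (assumed).
- m = failures that stay in the PPS (assumed).
- All N are in the FAS with known outcome, and there are no other PPS exclusions (assumed).

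**Formulas**
- FAS survival = (N − k − m)/N
- PPS survival = (N − k − m)/(N − k)
- PPS − FAS = (N − k − m) × [1/(N − k) − 1/N] = k(N − k − m)/(N(N − k))

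With m = 0 the difference reduces to k/N. With k = 0 it is zero whatever the value of m.

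**Survival, N = 40**

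| k | m | FAS | PPS | Difference (points) |
|---|---|---|---|---|
| 0 | 0 | 40/40 = 100% | 40/40 = 100% | 0 |
| 1 | 0 | 39/40 = 97.5% | 39/39 = 100% | 2.5 |
| 2 | 0 | 38/40 = 95.0% | 38/38 = 100% | 5.0 |
| 3 | 0 | 37/40 = 92.5% | 37/37 = 100% | 7.5 |
| 1 | 1 | 38/40 = 95.0% | 38/39 = 97.4% | 2.4 |
| 2 | 1 | 37/40 = 92.5% | 37/38 = 97.4% | 4.9 |
| 3 | 1 | 36/40 = 90.0% | 36/37 = 97.3% | 7.3 |

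If 50 patients were enrolled (assumed), the difference with m = 0 would be 1/50 = 2.0 points per loss.

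**Implant success.** Take k = 2 and two surviving but unsuccessful implants that complete Visit 7 (assumed). FAS = 36/40 = 90.0%, PPS = 36/38 = 94.7%, a difference of 4.7 points. Success is biased only through the lost implants, because the other non-successes stay in.

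**Is such a loss plausible?** The chance of at least one loss in 40 is 1 − (1 − p)^40. At assumed loss rates p of 2%, 5% and 10% this is 55%, 87% and 99%. Not every loss need lead to withdrawal before Visit 7.

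**The case against.** The strongest case is about weight. The primary analysis uses the FAS, which keeps patients who leave early. The PPS is only supportive, the study is descriptive, and no decision depends on the PPS. A reader would see 39/40 beside 39/39, and the reasons for withdrawal are recorded. The figures above come entirely from assumed counts, and other exclusions (missed visits, major deviations) could move the PPS in ways the table does not show. All of this stands. It limits the harm and is why the point ranks low, but it does not remove the fault: following the plan exactly still drops known failures from the supportive figures. Section 9.1.2 also names only the primary analysis for the FAS, while the secondary analyses are named only in section 9.1.3. The PPS may therefore carry more weight for implant success than the word supportive suggests.

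A second objection is that the repair needs a failure date, while the Study Termination page is only said to hold the reason for withdrawal. That is right as far as that page goes. However, implant loss and implant fracture are listed in Table 6 as expected device effects, and section 8.3.4 requires such effects on the AE eCRF page, so the date can be obtained there.

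A third is that section 11.3.6.1 gives omitted procedures as an example of a major deviation, so a patient excused later visits might be excluded on that ground instead. This is a fair drafting point and is met below.

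**Conclusion.** The concern holds. As written, sections 9.1.3 and 11.3.5 together exclude from the PPS every patient whose implant loss leads to withdrawal before Visit 7. Each such loss raises PPS survival and success above the values obtained with that patient counted as a failure. Under the stated assumptions the survival bias is about 2.5 points per loss with 40 implants, slightly less if some failures stay in the set. PPS survival reaches 100% only if every failure is withdrawn in this way, and there is no bias if none is. The primary FAS result is unaffected by this rule. It should be fixed because the correction is cheap, but it sits at the lower end of that category.

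**What to change.** Keep the completion requirement in section 9.1.3 and add text to this effect:

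> For a patient with documented implant failure as defined in section 7.14 up to Visit 7, completion is required only for visits whose Table 3 window closed before the failure date. Later visits are not required, and their absence is not a deviation for PPS purposes. The documented failure is the primary measurement. Unless excluded for another reason, the patient stays in the PPS and counts as failed for survival and not successful for implant success. PES and bone level are summarised on available measurements, with the number of patients stated.

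A patient who missed a visit due before the failure is then treated like a survivor who missed the same visit. Tying the rule to section 7.14 avoids the undefined term implant loss. The withdrawal rule in section 11.3.5 need not change. Under the assumptions used above, the PPS and FAS percentages become equal.

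**Cost.** A few sentences, no new visits and no new data: the reason for withdrawal is on the Study Termination page and the failure date can be taken from the AE page. Once the first patient has entered, section 11.8 requires a signed amendment, with ethics committee approval if the change is judged significant. There are two downsides. The supportive figures may look less favourable, and a small selection effect remains because a patient who fails early has fewer visits to miss.

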9.2 Missing Data

Every effort will be made to minimize the amount of missing data. If a patient drops out of the study prior to completing his/her primary endpoint assessment, the Investigator (or designee) will attempt to call the patient and to collect the information as detailed in Section 11.5.

10 Obligations of the Principal Investigator

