7.14 Implant Survival

Implant survival will be assessed at the time points listed in the schedule of assessment (Table 2).

A "surviving implant" is an implant stably inserted in the jaw. Note, that a surviving implant may not be successful if the success criteria (see Section 7.13) are not fulfilled.

A "failed implant" is an implant that:

- Has been removed; or
- Has fractured beyond repair.

[figure not shown]

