11.5 Patient Retention and Minimizing Loss to Follow-Up

If a patient does not return for any scheduled visits, the Investigator (or designee) will attempt to call the patient and reschedule the office appointment or document the patient's reason for not returning.

During the phone call, if the patient indicates that he/she no longer wishes to be in the study, information will be collected on reason for study withdrawal (e.g., lack of interest, moving, switching of dentist, AEs).

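### Read literally, the per-protocol set excludes implants lost before Visit 7, and the drop-out call need not ask whether the implant is still in place

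*Combined protocol and SAP*

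**What the plan says.** **Endpoint.** The primary endpoint is implant survival 12 months after placement (Section 3.4.1). Under Section 7.14 an implant has failed if it was removed or if it "Has fractured beyond repair". Survival is assessed at Visits 3 to 7 (Table 2). Section 9 is descriptive; for categorical data it plans "patient counts, frequencies and percentages for categorical variables".

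**Analysis sets.** The primary analysis uses the FAS on the intent-to-treat principle. The FAS holds patients who "received the study implant and from whom at least one follow-up measurement after baseline is available", and early termination does not remove them (Section 9.1.2). The PPS is supportive and requires that the patient "completed the study (Visit 1 to Visit 7) and the measurements of the primary variable is available" (Section 9.1.3).

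**Withdrawal.** Section 11.3.5 reads "The Investigator must withdraw any patient from the study in the case of" and gives implant loss as the one such case. Withdrawn patients are not replaced.

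**Missing data.** If a patient drops out before the primary assessment, Section 9.2 says that the Investigator or designee "will attempt to call the patient and to collect the information as detailed in Section 11.5". Under Section 11.5 the caller tries to "reschedule the office appointment or document the patient's reason for not returning". If the patient wants to leave the study, "information will be collected on reason for study withdrawal (e.g., lack of interest, moving, switching of dentist, AEs" is what the section adds.

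**The concern.** The PPS rule and the withdrawal rule work against each other. The event that the study is designed to count triggers withdrawal, and withdrawal before Visit 7 means that the seven visits are not completed. The supportive survival figure then loses failures because they failed, so agreement or disagreement between PPS and FAS says little about robustness.

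The call is a separate problem of data collection. It is the only stated route to the endpoint for a patient who has stopped attending, yet asking about the implant is not among its required contents. A loss comes to light only if the visit is rebooked or the patient happens to give it as the reason for leaving. Status that was not sought during follow-up is hard to recover at analysis. With a planned enrolment of at least 40, each such patient weighs as much in the reported figure as one observed loss.

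**Working it through.** **Inputs.** N = 40 is the minimum enrolment (Section 3.5), taken here as the FAS size. The protocol states neither a drop-out rate nor an expected survival rate, so known losses before Visit 7 (f) and patients of unknown 12-month status (d) are assumptions. There is no planned figure to reproduce, because Section 9 says that no formal sample size calculation was made. Intervals are exact (Clopper-Pearson) 95%.

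**1. The PPS rule**

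- Section 9.1.3 joins its conditions: Visits 1 to 7 completed, and the primary variable available. A lost implant has a known primary outcome, so it meets the second condition. A patient withdrawn at loss before Visit 7 does not meet the first.
- Patients of unknown status are outside the PPS under either reading. Nobody else is assumed to be excluded.
- Literal reading: (N − f − d)/(N − f − d) = 100% for any f.
- Losses kept: (N − f − d)/(N − d).

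| f | d | Literal PPS | Losses kept | Difference, f/(N − d) |
|---|---|---|---|---|
| 1 | 4 | 35/35 = 100% | 35/36 = 97.2% (85.5 to 99.9) | 1/36 = 2.8 points |
| 2 | 0 | 38/38 = 100% | 38/40 = 95.0% (83.1 to 99.4) | 2/40 = 5.0 points |
| 2 | 4 | 34/34 = 100% (89.7 to 100) | 34/36 = 94.4% (81.3 to 99.3) | 2/36 = 5.6 points |

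Two kinds of failure can still appear in the PPS: one first found at Visit 7, and an implant fractured beyond repair but not removed in a patient who stays in the study. Mandatory withdrawal is worded for implant loss, and Table 6 lists implant fracture separately from loss or failure of the implant.

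**2. Unknown status in the FAS**

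- A patient last seen at suture removal (day 7 to 14) qualifies for the FAS with about two weeks of known status.
- Known status only: (N − f − d)/(N − d). Unknowns as survivors: (N − f)/N. Unknowns as failures: (N − f − d)/N.
- Distance between the two bounds: d/N, or 1/40 = 2.5 points per unknown.

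| f | d | Known status | Unknowns survive | Unknowns fail | Distance between bounds |
|---|---|---|---|---|---|
| 0 | 4 | 36/36 = 100% (90.3 to 100) | 40/40 = 100% (91.2 to 100) | 36/40 = 90.0% (76.3 to 97.2) | 10.0 points |
| 2 | 4 | 34/36 = 94.4% (81.3 to 99.3) | 38/40 = 95.0% (83.1 to 99.4) | 34/40 = 85.0% (70.2 to 94.3) | 10.0 points |

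The bounds are limits, not expectations.

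**3. Why an estimator cannot replace the question**

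- If 2 losses occur with 40 at risk and 4 intact patients then leave for unrelated reasons, Kaplan-Meier gives 38/40 = 95.0%. The known-status proportion, 94.4%, is 0.6 points too low.
- If no loss is recorded but 2 of the 4 leavers lost the implant unseen, true survival is 38/40 = 95.0%. Known status (36/36) and Kaplan-Meier both show 100%. Only asking the patients, or reporting the bounds, reveals this.

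**The case against.** The best defence is that the primary analysis already handles the important cases. A known removal or irreparable fracture is a failure under Section 7.14 and stays in the FAS. Section 9.1.2 keeps early leavers, so the FAS itself is fixed. Survival is recorded at Visits 3 to 7, so each leaver has a known status up to the last visit attended. The reason for withdrawal goes on the Study Termination page (Section 11.3.5), and missing data are queried (Section 11.4.4). Counts will be reported, and a reader can derive the bounds from them. The PPS is only supportive.

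All of this stands and limits the point. It does not change the literal PPS definition, and none of these routes requires anyone to ask a departing patient about the implant. Adverse events are reviewed at visits (Section 7.16), which these patients no longer attend.

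Four stronger readings are tempting, but the documents do not support them:

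- *The PPS can contain a failure only if it is found at Visit 7.* An unremoved irreparable fracture is not plainly covered by mandatory withdrawal.
- *Implant losses vanish from the primary analysis.* Known losses remain in the FAS as failures.
- *Implant status of leavers is never collected.* The protocol does not require it on the call, but the eCRF and the Data Management Plan are not among the documents and might provide for it.
- *The primary denominator is free to be chosen afterwards.* Section 9.1.2 keeps early leavers in. What is open is how their unknown status is counted.

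**Conclusion.** The point holds in two parts. The PPS definition, combined with mandatory withdrawal, biases supportive survival toward 100% if read literally: by 5.6 points with 2 losses before Visit 7 and 4 unknowns among 40. The drop-out call leaves obtainable primary-endpoint data unrequested, and each unknown can move FAS survival by up to 2.5 points.

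The missing counting rule would, taken alone, be closer to an absent detail. It matters here because it meets a collection gap that cannot easily be repaired later. Leaving unknowns out overstates survival if withdrawal is implant-related, and can understate it slightly if intact patients leave for unrelated reasons.

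The sizes rest on an assumed FAS of 40 and assumed numbers of losses and unknowns. A reader might infer that the study's conclusion could be reversed. With no hypothesis test and no survival threshold, the effect is confined to the reported figure. The changes should be made, but the point does not invalidate the design.

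**What to change.** 1. **Section 9.1.3.** State that a patient with implant failure under Section 7.14 before Visit 7, otherwise eligible for the PPS, stays in it as a failure. The withdrawal rule itself need not change.
2. **Section 11.5.** On the planned call, if the visit cannot be rebooked and the patient agrees to answer, record whether the implant has been removed or has fractured, with the date, flagged as patient-reported. If the call comes before the 12-month window (12 months ± 1 month), ask permission for one further status call in or after it. Count an implant reported in place in or after that window as surviving at 12 months. Count a failure up to and including the Visit 7 assessment as a failure.
3. **Section 9.** Name one primary FAS estimate in advance, for example Kaplan-Meier at 12 months with censoring at last known status and in-window assessments treated as 12 months, or the known-status proportion. State the number with unknown status. Report both bounds (all unknowns as survivors, all as failures), and show the result with and without patient-reported status. Further estimates and an exact confidence interval are optional.

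**Cost.** One question on an existing call, possibly one further voluntary call, an eCRF field if none exists, a few lines of analysis code, and an amendment with ethics committee approval where Section 11.8 requires it. Self-report is less reliable than examination, and a patient may be unable to judge a fracture. Some patients will stay unknown, and anyone leaving must be free not to answer. The reported result may look less favourable.

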10.1 Investigator Compliance

The Investigators must work according to standard ethical practice as laid down by their professional body and insert the product according to what is described in the handling procedures and the IfU for the products investigated in this clinical study. In addition, they must work in accordance with the "Declaration of Helsinki" (last revision Fortaleza 2013, WMA General Assembly, 2013), the ISO 14155:2011, Good Clinical Practice (GCP) and with local legal and regulatory requirements.

The Investigators will ensure that the study is conducted in compliance with this protocol and the Clinical Study Agreement. Specifically, they are also responsible of conducting the informed consent process (Section **Error! Reference source not found.**).

11 Study Management

11.1 Insurance

As only CE-marked products are investigated, the product liability insurance applies.

11.2 Site Selection

The sites were selected by assessing e.g., training and experience of the site staff, site equipment, patient pool and expected recruitment period.

